1. SYNOPSIS

Name of Sponsor/Company: Rhythm Pharmaceuticals, Inc.	
Name of Investigational Product: Setmelanotide	
Name of Active Ingredient: Setmelanotide (RM-493; Melanocortin-4 Receptor Agonist)	
Title of Study: A Phase 2, Open-Label 20-Week Study to Evaluate the Safety and Efficacy of Setmelanotide in Subjects with Hypothalamic Obesity	
Study center(s): Approximately 3-5 clinical sites in the United States (US)	
Principal Investigator: [name]	
Studied period (years): Estimated date first patient enrolled: 26Feb2021 Estimated date last patient completed: 31Mar2022	Phase of development: 2
Objectives: Primary: The primary objective of this study is to evaluate the change in body weight in response to setmelanotide administered subcutaneously (SC) daily in patients with hypothalamic obesity (HO). Secondary: The secondary objectives of this study are to evaluate changes in parameters of body weight, body mass index (BMI), waist circumference, and hunger in response to setmelanotide in patients with HO and to evaluate the safety and tolerability of setmelanotide in patients with HO. 	
Methodology: This is a Phase 2, multicenter, open-label, proof of concept study designed to assess the effect of setmelanotide on weight loss on a population affected by HO. Approximately 15 patients aged 6 to 40 years, inclusive, are planned to be enrolled across approximately 3-5 clinical sites in the US.	
Screening Period Upon providing informed consent, patients will enter the Screening Period, during which they will be assessed for eligibility and complete all screening procedures as described in the Schedule of Activities (SoA).	
Treatment Period Patients who are determined to be eligible, based on Screening assessments, will return to the clinic for the Baseline Visit (Visit 2) and receive the first setmelanotide dose. The starting setmelanotide dose is dependent on patient age; however, for all patients, the setmelanotide dose will be titrated to a final dose of 3.0 mg/day (initial titration phase), as follows:	

Name of Sponsor/Company: Rhythm Pharmaceuticals, Inc.
Name of Investigational Product: Setmelanotide
Name of Active Ingredient: Setmelanotide (RM-493; Melanocortin-4 Receptor Agonist)

Patients aged 6 to <16 years, inclusive
 
Starting at Baseline (Day 1; Visit 2) through approximately Day 14, patients will receive setmelanotide 1.0 mg/day.Starting at approximately Day 15 through 28, patients will receive setmelanotide 2.0 mg/day. Patients/caregivers will be contacted by study center personnel on Day 15 to ensure dose titration has occurred and to document any adverse events (AEs).Starting on approximately Day 29 (Visit 3), patients will receive setmelanotide 3.0 mg/day; patients will continue to receive setmelanotide 3.0 mg/day for 12 weeks. 
The dose of setmelanotide should be titrated as explained in the SoA.
 
Patients aged ≥16 years, inclusive
 
Starting at Baseline (Day 1; Visit 2) through approximately Day 14, patients will receive setmelanotide 2.0 mg/day.Starting at approximately Day 15, patients will receive setmelanotide 3.0 mg/day; patients will continue to receive setmelanotide 3.0 mg/day for 14 weeks. 
The dose of setmelanotide should be titrated as explained in the SoA.
 
Patients will return to the study center for Visits 3, 4, and 5 (Weeks 4, 8, and 12, respectively), with each of these visits conducted approximately 4 weeks apart. All patients will return to the study center at Week 16 (Visit 6) and receive the last setmelanotide injection. Study endpoints are analyzed at Visit 6. After completion of Visit 6, participation in the current study will then conclude in one of the following 2 ways:
 
Patients meeting the primary endpoint may be eligible to be enrolled in a separate extension study, Rhythm Study RM-493-022, under which auspices the patient will continue to receive setmelanotide.Patients who do not meet the primary endpoint or elect not to continue setmelanotide are to discontinue setmelanotide at Visit 6 and return for an End-of-Study Visit (Visit 7) 4 weeks thereafter for a final safety review under the auspices of the current study.
Number of patients (planned): Approximately 15 patients are planned to be enrolled.

Name of Sponsor/Company: Rhythm Pharmaceuticals, Inc.
Name of Investigational Product: Setmelanotide
Name of Active Ingredient: Setmelanotide (RM-493; Melanocortin-4 Receptor Agonist)
Diagnosis and main criteria for inclusion: Inclusion Criteria Patients must meet all of the following criteria to be eligible for study participation: 
1. Patient has documented evidence of HO, including:
a. Recent (within the previous 8 months before Screening) evidence of hypothalamic injury on magnetic resonance imaging (MRI); ANDb. Diagnosis of craniopharyngioma or other non-malignant brain tumor affecting the hypothalamic region; ANDc. Has undergone surgery, or chemotherapy, or radiation ≥ 6 months and ≤ 15 years before Screening.2. Patient has either unilateral hypothalamic lesions (at least 6 patients) or bilateral hypothalamic lesions (at least 7 patients), as assessed by MRI. 
Note: Although the intention of the study is to enroll at least 6 patients with unilateral hypothalamic lesions, the Sponsor may decrease the required number during the course of the study.
 
3. Aged 6 to 40 years, inclusive, at time of enrollment. (A maximum of 10 patients between the ages of 6 and 12 will be enrolled in the study.)4. Obesity, documented by a BMI ≥ 35 kg/m² for patients ≥ 18 years of age or BMI ≥ 95th percentile for age and gender for patients 6 to <18 years of age based on the US Centers for Disease Control and Prevention criteria.5. Documented increase in BMI (change from pre-surgery baseline in BMI Z-score ≥ 0.2 for patients <18 years of age or BMI $>5\%$ for patients ≥ 18 years of age) either during the first 6 months following surgery or within 1 year before surgery AND still present at Screening.6. More than 6 months after the end of post-tumor treatment, including chemotherapy, surgery, or radiation.7. Patient must meet one of the following contraception requirements:
• If a female of childbearing potential, defined as fertile, following menarche and until becoming post-menopausal unless permanently sterile (hysterectomy, bilateral salpingectomy, or bilateral oophorectomy), must use a highly effective form of contraception as outlined in Section 9.19.5.• If a female of non-childbearing potential, defined as permanently sterile (status post hysterectomy, bilateral oophorectomy, or bilateral salpingectomy) or post-menopausal for at least 12 months (and confirmed with a screening follicle-stimulating hormone [FSH] level in the post-menopausal laboratory range), contraception is not required during the study.• Younger female patients who have not reached menarche upon study entry will be assessed for Tanner staging and at first menarche will be required to comply with contraception requirements and pregnancy testing as outlined in the protocol.

Name of Sponsor/Company: Rhythm Pharmaceuticals, Inc.
Name of Investigational Product: Setmelanotide
Name of Active Ingredient: Setmelanotide (RM-493; Melanocortin-4 Receptor Agonist)

• If a male with female partner(s) of childbearing potential, must agree to a double barrier method if they become sexually active during the study. Furthermore, male patients must not donate sperm during and for 90 days following their participation in the study.8. Ability to communicate well with the Investigator, understand and comply with the requirements of the study, and understand and sign the written informed consent, or, for patients aged <18 years, a parent/legal guardian that can sign.9. If receiving hormone replacement therapy (ie, thyroid hormones, glucocorticoids, growth hormone or other medications known to affect metabolism or weight/body composition), the dose of such therapy has remained stable for at least 2 months prior to Screening. (Changes in dose of $\leq 15\%$ may be permissible, with the Sponsor's approval.)
Exclusion Criteria Patients meeting any of the following criteria are not eligible for study participation: 
1. Weight gain $>5\%$ in the previous 3 months.2. Weight loss $\geq 2\%$ in the previous 3 months. NOTE: Dietary and/or exercise regimens, with or without the use of medications, supplements or herbal treatments associated with weight loss (eg, orlistat, lorcaserin, phentermine, topiramate, naltrexone, bupropion, glucagon-like peptide-1 [GLP-1] receptor agonists, etc.) are allowed if:
• the regimen and/or dose has been stable for at least 3 months prior to randomization• the patient has not experienced weight loss $\geq 2\%$ during the previous 3 months, AND• the patient intends to keep the regimen and/or dose stable throughout the course of the study.3. Bariatric surgery or procedure (eg, gastric bypass/band/sleeve, duodenal switch, gastric balloon, intestinal barrier, etc) within the last 6 months. All patients with a history of bariatric surgery or procedures must be discussed with and receive approval from the Sponsor prior to enrollment.4. Diagnosis of severe psychiatric disorders (eg, schizophrenia, bipolar disorder, personality disorder), or Major Depressive Disorder (MDD) within the previous 2 years, or Screening Patient Health Questionnaire (PHQ)-9/PHQ-A score ≥ 15, or any suicidal ideation of type 4 or 5 on the Columbia-Suicide Severity Rating Scale (C-SSRS) during Screening, or lifetime history of suicide attempts, or any suicidal behavior in the last month.5. Glycated hemoglobin (HbA1c) $>10.0\%$ at Screening.6. Current, clinically significant pulmonary, cardiac, or oncologic disease considered severe enough to interfere with the study and/or confound the results. Any patient with a potentially clinically significant disease should be reviewed with the Sponsor to determine eligibility.7. Glomerular filtration rate (GFR) <30 mL/min/1.73 m² during Screening.8. Significant dermatologic findings relating to melanoma or pre-melanoma skin lesions (excluding non-invasive basal or squamous cell lesion), determined as part of a comprehensive

Name of Sponsor/Company: Rhythm Pharmaceuticals, Inc.
Name of Investigational Product: Setmelanotide
Name of Active Ingredient: Setmelanotide (RM-493; Melanocortin-4 Receptor Agonist)

skin evaluation performed by the Investigator during Screening. Any concerning lesions identified during Screening will be biopsied and results known to be benign prior to enrollment. If the pre-treatment biopsy results are of significant concern, the patient is not eligible for study participation.
 
9. History or close family history (parents or siblings) of skin cancer or melanoma (not including noninvasive, infiltrative basal or squamous cell lesion), or patient history of ocular-cutaneous albinism.
 
10. Participation in any clinical study with an investigational drug/device within 3 months or 5 half-lives, whichever is longer, prior to the first setmelanotide dose.
 
11. Previously enrolled in a clinical study involving setmelanotide or any previous exposure to setmelanotide.
 
12. Inability to comply with once daily (QD) injection regimen.
 
13. Pregnant and/or breastfeeding, or desiring to become pregnant during this trial.
 
14. Cognitive impairment that, in the Investigator's opinion, precludes participation to the study and completions of study procedures or questionnaires.
 
15. Patient is, in Investigator's opinion, otherwise not suitable to participate in the study.

Investigational product, dosage, and mode of administration: Investigational product: Setmelanotide, 10 mg/mL in a sterile solution for injection. Dosage: 1.0, 2.0, 3.0 mg QD for patients 6 to <16 years of age, and 2.0 to 3.0 mg QD for patients \geq 16 years of age. Mode of administration: SC injection
Duration of treatment: All patients will receive study treatment for 16 weeks. Total study participation will last between 22 and 28 weeks, based on the variable length of the Screening Period.
Reference therapy, dosage, and mode of administration: NA

Name of Sponsor/Company: Rhythm Pharmaceuticals, Inc.
Name of Investigational Product: Setmelanotide
Name of Active Ingredient: Setmelanotide (RM-493; Melanocortin-4 Receptor Agonist)
Criteria for evaluation: Primary endpoints: 
Proportion of patients with $\geq 5\%$ reduction from baseline in BMI after 16 weeks of setmelanotide treatment compared to a historic control of $< 5\%$ in this patient population. Key Secondary Endpoints: 
Composite proportion of patients aged ≥ 6 to < 18 years with ≥ 0.2 reduction of BMI Z-score and patients aged ≥ 18 years with 5% reduction of body weight from baseline after 16 weeks of setmelanotideProportion of patients aged ≥ 6 to < 18 years with ≥ 0.2 reduction of BMI Z-score from baseline after 16 weeks of setmelanotideProportion of patients aged ≥ 18 years with $\geq 5\%$ reduction of body weight from baseline after 16 weeks of setmelanotide Other Secondary Endpoints: 
Change from baseline in waist circumference in patients aged ≥ 18 years after 16 weeks of setmelanotide treatment.Change in hunger in response to 16 weeks of setmelanotide treatment as measured by change from baseline in daily and global hunger scores.Safety and tolerability assessed by the frequency and severity of AEs, vital signs, and laboratory evaluations.  Statistical methods: The study is a Phase 2, Proof-of-Concept study. The objective of this study is to evaluate safety and preliminary efficacy on weight loss in patients with HO. The primary endpoint is the proportion of patients who achieve at least 5% reduction from baseline in BMI at ~16 weeks of treatment with setmelanotide. Given the exploratory nature of the study, the sample size is primarily driven by clinical considerations, with the consideration of statistical testing. It is planned to enroll ~5 to 10 patients aged ≥ 12 years, and up to 10 patients between 6 and < 12 years. With 10 patients aged ≥ 12 years and up to

Name of Sponsor/Company: Rhythm Pharmaceuticals, Inc.
Name of Investigational Product: Setmelanotide
Name of Active Ingredient: Setmelanotide (RM-493; Melanocortin-4 Receptor Agonist)
10 patients aged 6 to <12 years, at 1-sided 0.05 significance level, the study provides ~90% power to reject the null hypothesis that the true response rate is less than 5%, assuming a 40% target response rate in setmelanotide.

2. SCHEDULE OF ACTIVITIES

The schedule of activities (SoA) is presented in [Table 1](#).

Table 1: Schedule of Activities

Study Period/Procedure	Screening	Study Treatment						EOS Visit	Treatment Discontinuation Visit
		V1	V2	-	V3 ¹	V4	V5	V6 ²	
Clinic Visit Number									
Study Day	-56 to -14	1	15	29	57	85	113	141	
Visit Window (days)	-	-	+3d	±4 d					
Informed consent/assent ³	X								
Inclusion/exclusion criteria review	X	X							
Medical history review	X								
Physical examination ⁴	X	X		X	X	X	X	X	X
Comprehensive skin examination ⁵	X						X		X
Fitzpatrick classification scale	X						X	X	X
Weight ⁶	X	X		X	X	X	X	X	X
Waist circumference ⁷	X	X		X	X	X	X	X	X
Height ⁸	X			X	X	X	X	X	X
Body composition assessment by DXA ⁹	X						X		X
Vital signs ¹⁰	X	X		X	X	X	X	X	X
ECG (12-lead) ¹¹	X	X ¹¹		X ¹¹			X ¹¹		X
Pregnancy test ¹²	X	X ¹³		X	X ¹³	X ¹³	X ¹³		X
Daily hunger questionnaires ^{14, 15}	X								X
Global hunger assessment ¹⁵		X ¹³		X ¹³	X ¹³	X ¹³	X ¹³	X	X
PHQ-A or PHQ-9 ^{16, 17}	X	X ¹³		X ¹³	X ¹³	X ¹³	X ¹³	X	X
C-SSRS ¹⁸	X	X ¹³		X ¹³	X ¹³	X ¹³	X ¹³	X	X
SF-12 or SF-10 ¹⁹	X	X ¹³		X ¹³			X ¹³		X
IWQOL-Lite-CT ²⁰	X	X ¹³		X ¹³			X ¹³		X

Study Period/Procedure	Screening	Study Treatment						EOS Visit	Treatment Discontinuation Visit
Clinic Visit Number	V1	V2	-	V3 ¹	V4	V5	V6 ²	V7 ²	
Study Day	-56 to -14	1	15	29	57	85	113	141	
Visit Window (days)	-	-	+3d	±4 d					
EQ-5D-5L or Y ²¹	X	X ¹³		X ¹³			X ¹³		X
Safety laboratory tests ²²	X	X		X ¹³	X ¹³	X ¹³	X ¹³	X	X
FSH*	X								
Injection site inspection ²⁴		X		X	X	X	X		X
Telephone call ²⁵			X						
Review lesion type on MRI ²⁶	X								
Study drug administration ²⁷		Daily dosing							
Dispense/Return study drug ²⁸		X		X	X	X	X		
Adverse event assessment ²⁹	X	X	X	X	X	X	X	X	X
Concomitant medications review	X	X	X	X	X	X	X	X	X

Abbreviations: C-SSRS = Columbia-Suicide Severity Rating Scale; D = Days; DXA = Dual-energy X-ray absorptiometry; ECG = electrocardiogram; EOS = End of Study; EQ-5D = EuroQol-5 Dimension; IWQOL-Lite-CT = Impact of Weight on Quality of Life-Lite Clinical Trials version; FSH = follicle-stimulating hormone; [REDACTED] MRI = magnetic resonance imaging; PHQ = Patient Health Questionnaire; SF= Short Form; V = Study Visit Number.

1. Patients who are <16 years of age will receive first daily dose of 3.0 mg at V3, at the clinic.
2. Study endpoints are analyzed at V6. After completing V6. Patients meeting the primary endpoint may be eligible to be enrolled in a separate extension study, Rhythm Study RM-493-022, under which auspices the patient will continue to receive setmelanotide. Patients who do not meet the primary endpoint or elect not to continue setmelanotide are to discontinue setmelanotide at Visit 6 and return for an End-of-Study Visit (Visit 7) 4 weeks thereafter for a final safety review under the auspices of the current study.
3. Although the study procedures and assessments required per protocol are classified as “No or Minimal Risk” (with the exception of DXA which may be classified as “Minor Increase over Minimal Risk”) according to the 2008 Guidance Document “Ethical Considerations for Clinical Trials on Medicinal Products Conducted with the Pediatric Population,” considerations for reducing pain in distress in patients younger than 18 years of age are included in [Appendix 2](#).

4. A complete physical examination will be conducted at Screening and at the EOS V7. At other time points, an abbreviated examination will be performed. The abbreviated examination should focus on heart, lungs, skin, neurologic exam, and any areas of previous abnormal findings, noting any changes from baseline. In addition, Tanner Staging for assessment of pubertal development will be conducted for those patients who have yet to reach Tanner Stage V. Whenever possible, the same trained health care professional will conduct the exam and Tanner Staging.
5. A comprehensive skin examination will be performed by the Investigator. The skin examination should include a full body (head-to-toe skin examination). If any concerning lesions are identified during Screening, the patient should be referred to a dermatologist. Any concerning lesions will be biopsied by the dermatologist and results must be benign prior to the first dose of setmelanotide. If the pre-treatment biopsy results are of concern, the patient will be excluded from the study. Additionally, any concerning lesion or change in an existing lesion during the course of the study must be evaluated by the dermatologist and biopsied, if clinically indicated in the opinion of the dermatologist.
6. Weight (kg) is to be measured at the clinic using the same scale throughout the study, including the Screening Visit, after patients have emptied their bladders and pockets and after fasting for at least 8 hours. Patients are to wear light clothing or underwear and no shoes, and will be weighed at approximately the same time of day. Weight should be recorded to the nearest tenth of a decimal place if reported by a digital scale or to the nearest half of a kg if reported by a mechanical scale.
7. Waist circumference (cm) will be done in triplicate and recorded to the nearest half cm. Waist circumference should be measured after patients have fasted for at least 8 hours and at approximately the same time at each visit. Patients should be standing and in light clothing and have emptied their bladder. Whenever possible, the same study staff member should perform the measurement for a given patient to minimize variability.
8. For patients ≥ 18 years of age, height needs to be measured at Screening only. Height (cm) will be measured, without shoes, socks, or hats, using a wall-mounted stadiometer. All measurements will be done in triplicate at each time point and recorded to the nearest half cm.
9. Body composition assessment will be performed using DXA. If DXA is not available at the clinic, this procedure may be skipped, with prior approval of the Sponsor.
10. All blood pressure (BP) and heart rate (HR) measurements are to be obtained with the patient in the sitting position following at least 5 minutes of rest. All measurements will be taken in triplicate, approximately 2 minutes apart. When possible, BP should be taken in the non-dominant arm throughout the study, using the same methodology (automated or manual). Body temperature ($^{\circ}\text{C}$) and respiration rate (breaths/minute) will be obtained in the sitting position following at least 5 minutes of rest.
11. A single 12-lead ECG will be performed in the supine position following a period of at least 10 minutes of rest. At V2, the ECG will be performed before and 4 hours after dosing, and at V3 and V6, the ECG is to be performed at 4 hours after dosing.
12. A urine pregnancy test may be performed to expedite availability of results prior to dosing on Day 1. All other pregnancy tests will be serum tests; dosing may continue with results pending.
13. Collected prior to study drug administration.
14. Daily hunger questionnaire scores will be recorded prior to the patient's morning meal. During Screening, the patient must complete the daily hunger questionnaire in the electronic diary at least 4 of the 7 days prior to V2, paper version can be used if required. Patients who do not meet this requirement should not be enrolled into the study. V2 may be rescheduled if needed to fulfill this requirement with Sponsor approval.
15. [REDACTED]
16. In order to be eligible for the study, an individual patient's PHQ-A or PHQ-9 score must be < 15 at Screening. If at any time during the study an individual patient's PHQ-A or PHQ-9 score is ≥ 10 , the patient should be referred to a Mental Health Professional (MHP).
17. The PHQ-A will be administered to patients 11-17 years old and the PHQ-9 will be administered to patients ≥ 18 .
18. In order to be eligible for the study, a patient at Screening cannot have a suicidal ideation of type 4 or 5, any lifetime history of a suicide attempt, or any suicidal behavior in the last month. If at any time during the study a patient has a suicidal ideation of type 4 or 5, or any suicidal behavior, the patient should be referred to an MHP.
19. The SF-12 will be administered to patients ≥ 18 years of age and the SF-10 will be administered to the parents/caregivers of patients < 18 years of age.

20. IWQOL-Lite-CT will be administered to patients ≥ 18 years of age.
21. The EQ-5D-5L will be administered to patients ≥ 16 years of age. The EQ-5D-Y will be administered to patients >8 up to <16 years of age. In patients under the age of 8 years of age will not complete the EQ-measures.
22. Safety laboratory tests will include: complete blood count with differential (platelet count, red blood cell [RBC] count, hemoglobin, hematocrit, neutrophils, lymphocytes, monocytes, eosinophils, basophils) and standard indices (mean corpuscular volume, mean corpuscular hemoglobin, %reticulocytes), chemistry panel (includes sodium, potassium, chloride, CO_2 , albumin, total protein, glucose, BUN, creatinine, uric acid, AST, ALT, GGT, CPK, alkaline phosphatase, total bilirubin, direct bilirubin, LDH, calcium, phosphorus), and urinalysis with microscopic analysis if positive findings on dipsticks warrant further examination.
23. Blood samples will be collected prior to dose administration in the fasting state for total cholesterol, high-density lipoprotein cholesterol, low-density lipoprotein cholesterol, and triglycerides.
24. Injection site evaluations and scoring (by the clinical staff) will include identification and measurement of areas of erythema, edema, and induration, as well as the presence of localized pain, tenderness, and itching. Additional evaluation data can be collected at any visit in which there are injection site reactions, even if not a time point for formal assessment.
25. Site personnel will call the patient on Day 15 to confirm the proper dose escalation has occurred and to collect AEs.
26. All patients must have evidence of hypothalamic injury on MRI completed within 8 months of Screening. If no MRI is available, then it may be repeated during the Screening Period.
27. Patients/caretakers will draw up and self-administer/administer the drug once daily in the morning beginning the morning of Day 1 and for the duration of dosing. On days with clinic visits, the patients/caretakers will administer the drug in the clinic in the presence of the clinical staff to assure proper technique.
28. Patients/caretakers will return all (the number recorded) used vials to the clinic when they visit, and both clinic-administered study drug as well as outpatient study drug administration will be recorded in a study diary.
29. AEs will be recorded from the time a patient provides informed consent. AEs reported after dosing on Day 1 will be considered TEAEs.

* FSH should be measured in women who have been post-menopausal >12 months and should be in post-menopausal range.

TABLE OF CONTENTS

TITLE PAGE	1
1. SYNOPSIS	4
2. SCHEDULE OF ACTIVITIES	11
3. INTRODUCTION	20
3.1. Rationale for the Study	20
3.2. Setmelanotide	21
3.3. Benefit/Risk Assessment	22
4. OBJECTIVES AND ENDPOINTS	24
5. STUDY DESIGN	25
5.1. Overall Design	25
5.2. Patient and Study Completion	26
5.3. Scientific Rationale for Study Design	27
5.4. Justification for Dose	27
5.5. Study Conduct During the COVID-19 (Coronavirus) Pandemic	28
6. STUDY POPULATION	28
6.1. Inclusion Criteria	28
6.2. Exclusion Criteria	29
6.3. Lifestyle Restrictions	31
6.4. Screen Failures	31
7. TREATMENTS	31
7.1. Treatments Administered	31
7.2. Method of Treatment Assignment	31
7.3. Dose Modification	32
7.4. Blinding	32
7.5. Preparation/Handling/Storage/Accountability	32
7.6. Assessment of Treatment Compliance and Study Drug Accountability	33
7.7. Concomitant Therapy	33
7.7.1. Prohibited Medications	33
7.8. Treatment after the End of the Study	34
8. DISCONTINUATION/WITHDRAWAL CRITERIA	34
9. PATIENT ASSESSMENTS	35

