Finally, chronic toxicology, reproductive, and juvenile toxicology studies using the RM-493-mPEG/DSPE formulation are completed and reports are in preparation.

The most significant potential safety issue for MC4R agonist compounds is the concern about potential mechanism-based increases in HR and BP. An MC4R agonist, LY2112688 (Eli Lilly and Company), had been studied in the clinic and caused HR and BP increases at all doses (eg, up to a mean 9.4 mm Hg increase in systolic BP [SBP] at the highest dose) [Greenfield 2009, Kievit et al 2013]. While the increases were not an immediate safety concern for the healthy volunteers in the Lilly study, similar but chronic increases in a patient population with obesity would have been problematic.

Setmelanotide was developed in nonclinical studies to analyze and obviate these cardiovascular (CV) effects. A large number of nonclinical studies were performed to demonstrate that setmelanotide did not cause similar CV effects as LY2112688, while still delivering equal or greater efficacy in animal models. The underlying premise of the development program was that setmelanotide in humans would deliver efficacy on weight loss without unacceptable CV effects.

A review of the clinical effects of setmelanotide revealed little if any evidence of BP or HR change from baseline versus placebo in any study, nor evidence of a pharmacokinetic/pharmacodynamic relationship [[Gottesdiener 2015](#)].

Other potential safety and/or tolerability issues that have been reported from published literature for some MC4R agonists in clinical and animal studies have included nausea and vomiting, male penile erections, increases in female sexual arousal, and off-target activity at the closely related MC1R (which mediates melanin deposition in the skin, producing tanning). In addition to careful CV monitoring, the setmelanotide program was designed to include careful monitoring for these potential mechanism-based effects in the initial clinical studies.

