9.12. Electrocardiograms

A single 12-lead ECG will be performed at the time points designated in the SoA ([Table 1](#)). ECGs are to be performed with the patient in the supine position following a period of at least 10 minutes of rest. At Visit 2, the ECG will be performed before and 4 hours after dosing, and at Visit 3 and Visit 6, the ECG will be performed at 4 hours after dosing.

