## 10.6 Electrocardiograms

The ECG measurements (described in [Section 3.5.4](#)) at Visit 2 (pre and post-dose), Visit 3, Visit 6, and the changes from pre-dose baseline will be summarized descriptively at each visit. In addition, a shift table will be created to show any change from pre-dose baseline to each visit in the overall ECG interpretation.

QTcF interval prolongation will be presented separately as well. The number and percentage of patients with a QTcF interval of >450 msec, >480 msec, and >500 msec will be summarized by visit, along with the number and percentage of patients with a change from pre-dose baseline in QTcF interval of 30 - < 60 msec and  $\geq 60$  msec.

All ECG results will be presented in a data listing. The listing will show the assessment date, ECG measurement, indicator ECG was not done (if applicable), reason ECG was not done (if applicable) ECG value, the change from baseline.

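### The V3 and V6 ECGs are taken 4 hours after the morning dose but compared with a pre-dose ECG, so the descriptive heart-rate and QTcF changes mix drug effect with time of day and uncontrolled meal state

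*Protocol*

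**What the plan says.** **Timing of the ECGs.** Protocol Section 2, footnote 11, sets one recording per time point: "A single 12-lead ECG will be performed in the supine position following a period of at least 10 minutes of rest". For the baseline visit, "At V2, the ECG will be performed before and 4 hours after dosing". For the later on-drug visits, the footnote continues: "at V3 and V6, the ECG is to be performed at 4 hours after dosing". Section 9.12 has the same rule: "at Visit 3 and Visit 6, the ECG will be performed at 4 hours after dosing". The Schedule of Activities also has an ECG at Screening and at the Treatment Discontinuation visit, neither with a stated time of day, and none at V7.

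**Timing of the dose.** Footnote 27 has the drug given "once daily in the morning beginning the morning of Day 1 and for the duration of dosing", in the clinic on visit days. The 4-hour ECG therefore falls in the late morning or early afternoon.

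**Comparison.** For the ECG measures, SAP 10.6 reads: "Visit 3, Visit 6, and the changes from pre-dose baseline will be summarized descriptively at each visit". The interpretation shift table and the QTcF change categories use the same pre-dose reference. The counts above 450, 480 and 500 msec use no reference. SAP 3.5.4 lists heart rate among the ECG measures. Protocol 10.3 and SAP 4.3 define baseline as the last value before the first dose.

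**Control.** Protocol 5.3 plans no placebo group.

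**The concern.** A change from a pre-dose morning ECG to an ECG 4 hours later contains whatever heart rate and QTcF would have done over those hours without drug. In a controlled trial the other arm would show that shift. Here nothing does.

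Meal state may add to it. Section 9 orders procedures that share a time point as vital signs, ECG, then blood draws, and Section 9.13 requires the draws to be pre-dose after an 8-hour fast. The V2 pre-dose ECG is therefore probably fasted. No rule covers food between the dose and the 4-hour ECG.

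What is at stake is how the cardiac safety read-out is interpreted. Section 3.2 names as the leading safety issue for the class the "concern about potential mechanism-based increases in HR and BP", and the 4-hour ECG is the only heart-rate reading fixed to a stated time after dosing. A drug-free rise would look like a drug effect, and a drug-free fall would hide one.

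**Working it through.** The documents give no precision or power figure for ECG, so there is no planned figure to reproduce.

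**1. What the planned ECGs can identify.** Let m be the drug-free mean at the pre-dose time, s the drug-free shift to the 4-hour time, and d2, d3, d6 the drug effects at V2, V3 and V6.

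| ECG | Expected value |
|---|---|
| V2 pre-dose | m |
| V2 4-hour | m + s + d2 |
| V3 4-hour | m + s + d3 |
| V6 4-hour | m + s + d6 |

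Four readings carry five unknowns, and the rank of this system is 4.

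- The planned V6 change is (m + s + d6) - m = s + d6. The bias is s, whatever the number of patients. The V3 and V2 4-hour changes carry the same bias.
- V6 minus V2 4-hour is d6 - d2. The shift cancels, but only the change beyond the first dose remains.
- The Screening ECG is drug-free, but its time is not set, so it equals neither m nor m + s by design.
- A drug-free ECG at the matching time and meal state has expected value m + s. Adding it raises the rank to 5. Then V6 minus that ECG is d6, provided m and s stay constant from Screening to Week 16.

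**2. Heart rate.** n = 15 is the planned enrolment (Protocol 5.1). The shift and the SD of change are assumptions.

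SE = SD / sqrt(15): 8 / 3.873 = 2.07 bpm and 10 / 3.873 = 2.58 bpm. Bias in SE units = shift / SE.

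| Assumed shift | SD 8 | SD 10 |
|---|---|---|
| 2 bpm | 0.97 | 0.77 |
| 5 bpm | 2.42 | 1.94 |
| 8 bpm | 3.87 | 3.10 |

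**3. QTcF change of 30 msec or more.** Shift and SD are again assumed. For a patient with no drug effect, P = 1 - Phi((30 - shift) / SD), and the expected number among 15 patients is 15 x P.

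| Assumed shift | P, SD 10 | Expected of 15 | P, SD 15 | Expected of 15 |
|---|---|---|---|---|
| 0 msec | 0.0013 | 0.02 | 0.0228 | 0.34 |
| 3 msec | 0.0035 | 0.05 | 0.0359 | 0.54 |
| 5 msec | 0.0062 | 0.09 | 0.0478 | 0.72 |
| 10 msec | 0.0228 | 0.34 | 0.0912 | 1.37 |

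The excess over no shift runs from 0.03 patients (3 msec, SD 10) to 1.03 patients (10 msec, SD 15). For 60 msec or more, even the largest case gives 1 - Phi((60 - 10) / 15) = 1 - Phi(3.33), about 0.0004 per patient, which is negligible.

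A negative shift works the other way. With a true effect of 30 msec, a shift of -5 msec lowers the chance of a reading at 30 msec or more from 0.50 to 0.31 (SD 10) or 0.37 (SD 15).

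**The case against.** **ECG carries little formal weight.** It is not among the safety endpoints in SAP 10.1, which are adverse events, vital signs and laboratory evaluations. SAP 10.6 is descriptive and plans no test. This stands. The standard errors above are only a yardstick for how large the bias is beside sampling noise.

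**Heart rate is measured elsewhere.** It is taken in triplicate as a vital sign at every clinic visit, and the procedure order in Section 9 suggests that this happens before dosing. A reader might infer that the trial cannot assess heart rate at all. The documents do not support that. They also fix no time after dosing for the vital signs, so these do not replace the 4-hour reading.

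**Earlier data are reassuring.** Section 3.2 reports little if any heart-rate change against placebo in previous studies, and it names no QT concern. This lowers the prior worry. Hypothalamic obesity is, however, a population not studied before (Section 3.3), and that comparison with placebo is not available here.

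**Food.** A reader might infer that the pre-dose ECG is fasted and the 4-hour ECG fed. The documents state neither. They support only that meal state before the 4-hour ECG is uncontrolled.

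**A Screening reference has its own faults.** It is a single reading, 14-56 days before Day 1. Making it the main baseline would conflict with Protocol 10.3 and SAP 4.3. This stands, and it is why the time-matched reference should be supplementary.

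**Single-arm changes never isolate a drug effect.** That is true in general. This component of the confounding, however, comes from the timing rule and can be reduced without a control arm.

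**Conclusion.** The mismatch is in the text. The planned ECG changes at V3 and V6, the interpretation shift table and the QTcF change categories estimate drug effect plus a drug-free shift that the design cannot separate from it. The V2 4-hour change has the same problem. The absolute QTcF counts and the primary result are unaffected.

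Its size is unknown. Under the assumed shifts of 2-8 bpm and SDs of 8-10 bpm, the bias in mean heart-rate change is about 0.8-3.9 standard errors at n = 15. Under the assumed QTcF shifts and SDs, the excess at 30 msec or more is about one patient at most, and the 60 msec category hardly moves. If the true shift is near zero, little is lost.

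It would go too far to conclude that the trial's cardiac safety data are invalid, that a drug effect is being hidden, or that the pre-dose baseline should be dropped. This is an inexpensive improvement to a descriptive safety read-out.

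**What to change.** **Protocol Section 2, footnote 11, and Section 9.12.** Take the already scheduled Screening ECG at approximately the clock time at which that patient's 4-hour post-dose ECG is expected. Record clock time and fed or fasted state at every ECG. The listing described in SAP 10.6 gives the assessment date but neither of these, so add both.

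**SAP 10.6.** Keep the V2 pre-dose ECG as the baseline, consistent with Protocol 10.3 and SAP 4.3. Add, as supplementary descriptive summaries:

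- changes from the time-matched Screening ECG for V2 4-hour, V3 and V6;
- V3 and V6 minus the V2 4-hour ECG, labelled as time-matched but showing only change beyond the first dose.

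**Cost.** No ECG is added. The work is a short text change in each document, two recorded items per ECG and a few extra table rows. Because dosing is fixed only to the morning, each site must plan an expected dose time when it books Screening. That visit may run later in the day, including for young children. The added reference is a single ECG 14-56 days before Day 1 with its own between-day variation, and its meal state may still differ from that of the on-drug ECGs. Recording meal state makes such differences visible but does not remove them.
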